12-lead QTc Assessment		X	X	X													See Table 5 for details.	
Echocardiography or MUGA scan	X																Echocardiography or MUGA scan to evaluate cardiac left ventricular ejection fraction	
MRI (Chest, abdomen, pelvis) or CT scan if contrast can be given	X																At Screening and to confirm CR, and for PR and MR if extramedullary disease detected at baseline, CT with contrast only if renal activity allows. If performed by PET/CT or MRI, osteolytic lesions and extramedullary disease can be evaluated within the same imaging.	

Assessments & Procedures	Screening	Intervention Period												End of Study Intervention	Follow-Up/ Discontinuation	Notes		
		up to 28 days before Day 1 Cycle 1		Cycle 1		Cycle 2		Cycle 3		Cycle 4		Cycle 5		Cycle 6		Every cycle after Cycle 6		
	Day	1	2	8	15	22	1	8	15	22	1	15	1	1	1	within 7 days after last intervention/intake	30 days after last dose	d = days
Visit Window			\pm 1 d	\pm 3 d	\pm 3 d	\pm 3 d	\pm 7 d	\pm 3 d	\pm 7 d									
Study Intervention M3258		<	-	-	-	-	-	-	-	-	-	-	-	-	-	>	QD In case of toxicity which cannot be managed during treatment alternative dose and regimen will be tested: see Section 4.1. For dose modification, see Section 6.6. For PK and Pd see Table 5 for details.	
Antiviral Prophylaxis for Herpes Zoster (valacyclovir or acyclovir)		<	-	-	-	-	-	-	-	-	-	-	-	-	-	->	According to institutional guidelines	
AE & SAE Review		<	-	-	-	-	-	-	-	-	-	-	-	-	-	X	X	Until 30 days after the last dose
Concomitant Medication Review		<	-	-	-	-	-	-	-	-	-	-	-	-	-	X	X	

Assessments & Procedures	Screening	Intervention Period												End of Study Intervention	Follow-Up/ Discontinuation	Notes		
		up to 28 days before Day 1 Cycle 1		Cycle 1			Cycle 2			Cycle 3		Cycle 4	Cycle 5	Cycle 6	Every cycle after Cycle 6			
	Day	1	2	8	15	22	1	8	15	22	1	15	1	1	1	within 7 days after last intervention/intake	30 days after last dose	d = days
Visit Window		± 1 d	± 1 d	± 1 d	± 1 d	± 1 d	± 1 d	± 1 d	± 1 d	± 1 d	± 1 d	± 1 d	± 3 d	± 3 d	± 3 d	± 7 d	± 3 d	± 7 d
Laboratory Assessments (Details regarding local and central laboratory assessments to be found in Appendix 7 and the Laboratory Manual, respectively.)																		
Serum Pregnancy Test (WOCBP only) at Screening and in urine thereafter	X	X					X			X		X	X	X	X	X	X	See Appendix 7
Urinalysis	X	X							X			X	X	X Every 3 rd cycle	X	X	See Appendix 7	
Hepatitis B and C and HIV Screening	X																See Appendix 7	

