
 To determine safety, tolerability and the MTD (if observed) of M3258 as a single agent in participants with RRMM 	
 Occurrence of DLTs in participants with RRMM receiving M3258 as a single agent during the DLT period Occurrence of any AEs reported (serious or nonserious) will be considered TEAEs and TRAEs (including TEAEs leading to death or discontinuation of treatment) in participants receiving M3258 as a single agent from start of study intervention to 30 days after End of Study Intervention Occurrence of TEAEs outside of the DLT period that SMC deems relevant for determination of the MTD Study treatment-emergent changes in clinical laboratory measures from Baseline, safety ECGs measures, vital signs, ECOG performance status in participants receiving M3258 as a single agent from start of study intervention to 30 days after end of study intervention
Secondary	

 To investigate the PK profile of M3258 (single and multiple dose exposure) in participants with RRMM 	
 PK profile of M3258 in terms of C_{max}, AUC_{0-t}, AUC_{0-24} at Day 1, Cycle 1, (single dose): predose, 1, 2, 3, 4, 5, 6, 8 and 24 h after administration PK profile of M3258 in terms of C_{max}, AUC_{0-24} at Day 8 Cycle 1, (multiple dose): predose, 1, 2, 3, 4, 5, 6, and 8 h after administration

 To investigate the recommended dose and regimen for expansion (RDE) in participants with RRMM 	
 In addition to safety, tolerability and PK, for selection of recommended dose and regimen for expansion (RDE), changes in Pd (LMP7 activity) in pre and post study intervention samples on Day 1 Cycle 1 pre and postdose, Day 2 Cycle 1 predose and Day 8 Cycle 1 pre and postdose

Objectives	Endpoints (Outcome Measures)
	
 Changes from Baseline in serum M-protein, urine M-protein, or free light chain protein levels (for free light chain disease) on Day 1 of every cycle

 To evaluate preliminary clinical activity using IMWG criteria 	
 OR, DOR, Time to Response until CR, sCR, VGPR or PR according to IMWG
Exploratory	

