4.1 Overall Design

This is a Phase I, open-label, FiH, 2-part (dose escalation and expansion), noncontrolled, multicenter clinical study designed to determine the safety, tolerability, PK, Pd and early signs of efficacy of M3258 as a single agent and co-administered with dexamethasone in participants with RRMM whose disease has progressed following > 3 prior lines of therapy and for whom no effective standard therapy exists (Figure 1).

The dose escalation phase is aimed at determining the recommended dose and regimen for the expansion phase (RDE) and the MTD based on safety, tolerability, PK, Pd (including LPM7 activity) and initial efficacy data of M3258 as a single agent. Following the dose-escalation phase, the safety and tolerability of M3258 with dexamethasone will be investigated in an expansion cohort of approximately 30 participants in addition to assessment of early clinical activity. If the dose is modified during the expansion phase, this sample size will increase by approximately 3-21 participants.

Each phase of the study will include a Screening period of up to 28 days, a study intervention period consisting of 21- or 28-day cycles of either M3258 alone (Part A) or M3258 in combination with dexamethasone (Part B), an End of Study Intervention visit (within 7 ± 3 days), and a Safety Follow-Up period of 30 (± 7) days. In Part B, participants will be followed up until 6 months after the last-participant-last-study-intervention intake. Participants who tolerate M3258 \pm combination with dexamethasone without significant clinically relevant toxicities may continue to receive their assigned dose if there is no evidence of confirmed disease progression (Section 4.4). Participants who discontinue study intervention for any reason will complete the End of Study Intervention and Safety Follow-Up visits.

Screening Period

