8.3 Adverse Events and Serious Adverse Events

The definitions of an AE and a SAE are in [Appendix 5](#).

8.3.1 Time Period and Frequency for Collecting Adverse Event and Serious Adverse Event Information

The AE reporting period for safety surveillance begins when the participant is initially included in the study (date of first signature of informed consent/date of first signature of first informed consent) and continues until the 30-Day Follow-Up Safety Visit.

Any SAE assessed as related to study intervention must be recorded and reported, as indicated in [Appendix 5](#), whenever it occurs, irrespective of the time elapsed since the last administration of study intervention.

The method of recording, evaluating, and assessing causality of AEs (including SAEs) and the procedures for completing and transmitting SAE reports are in [Appendix 5](#).

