9.4 Definition of On-treatment Period

The on-treatment period is defined as the time from first dose of study intervention to 30 days after end of study intervention, or the cut-off date, whichever occurs first.

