15.2 Adverse Events

AEs will be analyzed among the SAF analysis set and presented by regimen and dose (in increasing order) and summarized. Only participants counts will be presented with frequency.

Treatment-emergent adverse events (TEAE) are those events with onset dates occurring within the on-treatment periods as defined in section [9.4](#).

- **Related Adverse Events:** AEs with relationship missing, unknown or yes. Relationship is judged separately for M3258, and dexamethasone.
- **SAEs:** Serious adverse events (as recorded on the AE eCRF page, Serious Adverse Event = 'Yes').
- **AEs Leading to Treatment Discontinuation:** AEs leading to permanent discontinuation of study treatment (as recorded on the AE eCRF page, Action taken with study treatment = 'Drug withdrawn'). Treatment discontinuation is recorded separately for M3258, and dexamethasone.
- **AEs Leading to Death:** AEs leading to death (as recorded on the AE eCRF page, Outcome = 'Fatal').

All analyses described in Section [15.2](#) will be based on TEAEs if not otherwise specified.

TEAEs will be summarized by number and percentage of participants with at least one TEAE in the category of interest, by primary MedDRA and PT (both sorted alphabetically), unless otherwise stated. Each participant will be counted only once within each SOC or PT. If a participant experiences more than one AE within a SOC or PT for the same summary period, only the AE with the strongest relationship or the worst severity, as appropriate, will be included in the summaries of relationship and severity.

The severity of adverse events will be graded using the NCI-CTCAE version 5.0, except where CTCAE grades are missing. No imputation of missing grades will be performed.

Adverse events will be coded according to the latest MedDRA version at the time of the data cut-off.

Incomplete AE-related dates will be handled as defined in section [9.5](#).

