15.3 Adverse Events

The severity of adverse events will be graded using the NCI-CTCAE version 5.0, except where CTCAE grades are missing. No imputation of missing grades will be performed. Adverse events will be coded according to the latest MedDRA version at the time of the data cut-off.

- **TEAEs:** Any AEs that are reported (serious and non-serious) will be considered treatment emergent adverse events (TEAEs), with the exception of those that started prior to the first dose of study treatment (unless a worsening of the event is recorded after the first dosing, in which case the event will be counted as a TEAE), or AEs starting more than 30 days after the last dose of study treatment.
- **Related Adverse Events:** AEs with relationship missing, unknown or yes. Relationship is judged separately for M3258, and dexamethasone.
- **SAEs:** Serious adverse events (as recorded on the AE eCRF page, Serious Adverse Event = 'Yes').
- **AEs Leading to Treatment Discontinuation:** AEs leading to permanent discontinuation of study treatment (as recorded on the AE eCRF page, Action taken with study treatment = 'Drug withdrawn'). Treatment discontinuation is recorded separately for M3258, and dexamethasone.
- **AEs Leading to Death:** AEs leading to death (as recorded on the AE eCRF page, Outcome = 'Fatal').

AEs will be summarized by MedDRA PT as event category and MedDRA primary SOC as summary category. In general, each subject will be counted only once within each PT or SOC.

AEs with missing classifications regarding relationship to study treatment, and those with start date on or after the start of study treatment, will be considered as related to the study treatment.

Missing data handling

Incomplete AE-related dates will be handled as follows:

CCI

CONFIDENTIAL
INFORMATION

20/38

M3258

First in Human Dose Escalation of M3258 as a Single Agent and Expansion Study of M3258 in Combination with Dexamethasone

MS201814-0010

Version 2.0

- If the onset date is missing completely or missing partially – but the onset month and year, or year, are equal to that of the study treatment start – then the onset date will be replaced by the minimum of the start of study treatment and the AE resolution date.
- In all other cases, the missing onset day or month will be replaced by 1.

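### Protocol 8.3.1 and the Schedules of Activities give different ends of AE collection, and under 8.3.1 a follow-up visit before Day 30 cuts short the primary TEAE window

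*Protocol*

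**What the plan says.** The documents give the end of AE collection in two ways.

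- **Tied to a visit.** Protocol Section 8.3.1 says that the reporting period "continues until the 30-Day Follow-Up Safety Visit". Section 4.1 describes "a Safety Follow-Up period of 30 (± 7) days", and the follow-up column of Tables 1 to 4 carries the same ± 7 day window.
- **Tied to a day.** The note on the AE & SAE Review row in each of Tables 1 to 4 reads "Until 30 days after the last dose".

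The analysis window is tied to a day.

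- The Part A primary endpoint for TEAEs (Protocol Section 3, Table 7) covers participants on M3258 "as a single agent from start of study intervention to 30 days after End of Study Intervention". Table 8 uses the same window for Part B.
- SAP Section 9.4 defines the on-treatment period as "the time from first dose of study intervention to 30 days after end of study intervention", or to the cut-off date if that is earlier. Under SAP Section 15.2, TEAEs "are those events with onset dates occurring within the on-treatment periods".
- The SMC analysis plan (SAP Appendix 18.1, its Section 15.3) counts from the last dose. It excludes from TEAEs those "AEs starting more than 30 days after the last dose of study treatment".

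Two groups of events have their own rules. Section 8.3.1 makes SAEs judged related reportable at any time, and Section 8.3.3 requires AESIs to be reported throughout the study.

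**The concern.** A site that follows 8.3.1 may close AE reporting at a compliant visit on any of Days 23 to 29. A site that follows the schedule note would continue to Day 30. Both are following the protocol, yet they supply different observation windows for the same primary endpoint.

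The error can go in one direction only. A late visit (Days 31 to 37) adds nothing to the TEAE count, because the SAP stops counting at Day 30. An early visit can only remove time. SAP Section 15.2 reports numbers and percentages of participants and makes no allowance for a shortened window, so any effect lowers the reported incidence. Part A cohorts are planned at 3 participants. A single participant wrongly counted as free of an event type changes the cohort figure by 1/3, or 33 percentage points.

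**Working it through.** The plan gives no figure of its own to reproduce. The check is date arithmetic on the stated windows, with days counted from the last dose.

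**Inputs**

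- Follow-up visit: Day 30, window ± 7 (Protocol Section 4.1; Tables 1 to 4).
- End of collection: the visit (Section 8.3.1) or Day 30 (note in Tables 1 to 4).
- End of the TEAE window: Day 30, reading end of study intervention as the last dose (Protocol Section 3; SAP 9.4; the SMC plan).

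**Step 1: the gap under each rule.** Gap = end of TEAE window − end of collection, set to 0 if negative.

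| Visit held on | Gap under 8.3.1 | Gap under the schedule note |
|---|---|---|
| Day 30 − 7 = 23 | 30 − 23 = 7 days | 0 |
| Day 30 | 0 | 0 |
| Day 30 + 7 = 37 | 0 | 0 |

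The worst case is 7/30 = 23% of the post-treatment days. The whole TEAE window starts at first dose, so the share of that is smaller. For one 28-day cycle plus 30 days it is 7/(28 + 30) = 7/58 = 12%, and it falls with longer treatment.

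**Step 2: the average.** Visit dates are not given. Assume that they are spread evenly over the 15 days from 23 to 37.

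- Visits before Day 30: 7 of 15 = 47%.
- Days lost: 7 + 6 + 5 + 4 + 3 + 2 + 1 = 28.
- Mean loss: 28/15 ≈ 1.9 days per participant, and 1.9/30 ≈ 6% of the post-treatment days.

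If all visits fell on or after Day 30 the loss would be 0. If all fell on Day 23 it would be 7 days each.

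**Step 3: is there another route to capture?** Section 8.3.2 has AEs elicited by questioning at each study visit. Tables 1 to 4 schedule no AE contact after the follow-up visit. Part B adds only survival follow-up every 12 weeks. Section 4.4 ends Part A once participants have passed the Safety Follow-Up visit. The schedule note therefore sets the right end date but gives no means of reaching it after an early visit.

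**Step 4: which events are exposed?** After removing related SAEs and AESIs, what remains is mainly nonserious AEs that are not AESIs (including related ones, which count as TRAEs) and SAEs judged unrelated.

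**Step 5: the meaning of end of study intervention.** If it meant the End of Study Intervention visit (within 7 ± 3 days, so up to Day 10), the TEAE window would end as late as Day 10 + 30 = 40. The gap to a Day 23 visit would then be up to 17 days, and even the schedule note would fall 10 days short. The SMC plan's use of the last dose makes this the less likely reading, but neither the Protocol nor the main SAP rules it out.

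**The case against.** The strongest answer is that the schedule note is itself a collection rule. Section 8 of the Protocol makes adherence to the schedules mandatory, and under the note the gap is 0 days. That stands, and a reader should not infer from 8.3.1 alone that AE collection simply stops at Day 23. The documents support a contradiction between two rules. The note does not settle it, because 8.3.1 is the section that defines the reporting period, Section 8.3.2 and Appendix 5 tie recording and SAE reporting to that period, and no contact is scheduled to carry out the note after an early visit.

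The second answer is that the most important events are protected. Related SAEs have no time limit. AESIs, which include myelosuppression, GI toxicity, opportunistic infections and allergic reactions, are reported throughout the study. This also stands and narrows the point considerably.

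The third is that dose decisions are hardly touched, since DLTs are assessed in the first treatment cycle. That stands too. A visit 23 days after the last dose could precede the end of a 28-day cycle only if dosing stopped by about Day 4 (4 + 23 = 27).

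A reader might also infer that under-reporting is concentrated in participants who stop for progression or toxicity. Nothing in the documents shows that they attend earlier than others. Those are ordinary reasons for stopping in this trial, so no differential bias is shown.

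**Conclusion.** The point holds as an inconsistency between Protocol 8.3.1 and the AE & SAE Review row of Tables 1 to 4, with a limited effect on a primary endpoint. For a participant seen before Day 30, up to 7 days of the TEAE window may go uncollected. The average of about 1.9 days rests on the assumption of evenly spread visit dates. Both figures assume that the site follows 8.3.1 and that end of study intervention means the last dose. Any effect is downward and confined mainly to nonserious AEs that are not AESIs and to SAEs judged unrelated. The documents do not show that any event was missed. This is a minor defect and cheap to remove.

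**What to change.** - In Protocol 8.3.1, state that AEs are collected until the later of the follow-up visit and 30 days after the last dose, with a telephone contact at Day 30 if the visit was earlier. With this wording the gap is 0 for visits on Day 23, 30 or 37.
- Define end of study intervention as the last dose in the Protocol endpoints and in SAP 9.4, to match the SMC plan.
- In the primary analysis, list participants whose follow-up visit preceded Day 30, with the visit day. SAP Section 7 records that the study stopped before Part B began, so for data already collected this listing is the part that still helps.

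The cost is a sentence in the Protocol, a definition, one listing and an occasional telephone call. Changing the visit window to + 7 days only would also close the gap, but it removes scheduling freedom and is not needed if the call is added.

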8.3.2 Method of Detecting Adverse Events and Serious Adverse Events

At each study visit, the participant will be queried on changes in his or her condition. During the reporting period, any unfavorable changes in the participant's condition will be recorded as AEs, regardless if reported by the participant or observed by the Investigator.

Complete, accurate and consistent data on all AEs experienced for the duration of the reporting period (defined below) will be reported on an ongoing basis in the appropriate section of the eCRF. All SAEs and all nonserious AESIs must be additionally documented and reported using the appropriate Report Form as specified in [Appendix 5](#).

8.3.3 Follow-Up of Adverse Events and Serious Adverse Events

AEs are recorded and assessed continuously throughout the study, as specified in Section 8.3.1 and are assessed for their outcome at the 30-Day Follow-Up Safety Visit. All SAEs ongoing at

the 30-Day Follow-Up Safety Visit must be monitored and followed up by the Investigator until stabilization or until the outcome is known, unless the participant is documented as “lost to Follow-Up”. Reasonable attempts to obtain this information must be made and documented. It is also the responsibility of the Investigator to ensure that any necessary additional therapeutic measures and Follow-Up procedures are performed. Further information on Follow-Up procedures is given in [Appendix 5](#).

Based on the nonclinical toxicology studies, adverse events of myelosuppression, GI toxicity, opportunistic infections and allergic reactions are considered AESI (Section [6.9](#)). These events must be reported on AESI Forms to Merck Healthcare Global Patient Safety throughout the study until resolution or permanent outcome of the event.

8.3.4 Regulatory Reporting Requirements for Serious Adverse Events

The Sponsor will send appropriate safety notifications to Health Authorities in accordance with applicable laws and regulations.

The Investigator must comply with any applicable site-specific requirements related to the reporting of SAEs (particularly deaths) involving study participants to the Independent Ethics Committee/Institutional Review Board (IEC/IRB) that approved the study.

In accordance with ICH Good Clinical Practice (GCP), the Sponsor/designee will inform the Investigator of findings that could adversely affect the safety of participants, impact the conduct of the study or alter the IEC's/IRB's approval/favorable opinion to continue the study. In line with respective regulations, the Sponsor/designee will inform the Investigator of AEs that are both serious and unexpected and considered to be related to the administered product (“suspected unexpected serious adverse reactions” or SUSARs). The Investigator should place copies of Safety Reports in the Investigator Site File. National regulations regarding Safety Report notifications to Investigators will be considered.

When specifically required by regulations and guidelines, the Sponsor/designee will provide appropriate Safety Reports directly to the concerned lead IEC/IRB and will maintain records of these notifications. When direct reporting is not clearly defined by national or site-specific regulations, the Investigator will be responsible for promptly notifying the concerned IEC/IRB of any Safety Reports provided by the Sponsor/designee and of filing copies of all related correspondence in the Investigator Site File.

For studies covered by the European Directive 2001/20/EC, the Sponsor's responsibilities regarding the reporting of SAEs/SUSARs/Safety Issues will be carried out in accordance with that Directive and with the related Detailed Guidance documents.

8.3.5 Pregnancy

Only pregnancies the Investigator considers to be related to the study intervention (e.g., resulting from a drug interaction with a contraceptive method) are AEs. However, all pregnancies with an estimated conception date during the period defined in Section [8.3.1](#) (Time Period and Frequency for Collecting Adverse Event and Serious Adverse Event Information) must be recorded in the AE page/section of the eCRF for both pregnancies in female participants and pregnancies in female partners of male participants. The Investigator must notify the Sponsor/designee in an expedited manner of any pregnancy using the Pregnancy

Report Form, which must be transmitted by the same process specified for SAE reporting in [Appendix 5](#), section on Reporting Serious Adverse Events.

Investigators must actively follow up, document and report on the outcome of all these pregnancies, even if the participants are withdrawn from the study.

The Investigator must notify the Sponsor/designee of these outcomes using the Pregnancy Report Form. If an abnormal outcome occurs, the SAE Report Form will be used if the participant sustains an event and the Parent-Child/Fetus Adverse Event Report Form if the child/fetus sustains an event. Any abnormal outcome (e.g., spontaneous abortion, fetal death, stillbirth, congenital anomalies, ectopic pregnancy) must be reported in an expedited manner, as specified in Section [8.3.1](#), while normal outcomes must be reported within 45 days after delivery.

In the event of a pregnancy in a participant occurring during the study, the participant must be discontinued from study intervention. The Sponsor/designee must be notified without delay and the participant must be followed as indicated above.

